2.5 Conceptual framework

Figure 1 illustrates the conceptual framework for assessing tear quantity, corneal staining, and comfort levels during the wear of FDA contact lenses Group I, II, III, IV, and V materials.

2.6 **Objectives**

2.6.1 General Objectives:

The objective is to examine the impact of FDA contact lenses Group I, II, III, IV, and silicone hydrogel on tear assessment, corneal staining, and comfort levels among undergraduate students at UKM Kuala Lumpur Campus.

2.6.2 Specific Objectives:

i. Assessing tear quantity, corneal staining, and comfort levels before and after 8 hours of wearing FDA contact lenses Group I, II, III, IV, and silicone hydrogel.

ii. Contrasting tear evaluation and corneal staining pre- and post-8-hour application of FDA contact lenses Group I, II, III, IV, and silicone hydrogel.

iii. Comparing comfort levels pre- and post-8-hour wear among FDA contact lenses Group I,II, III, IV, and silicone hydrogel (Va and Vb).

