3.1.9 Study Protocol

Participants for this study will be recruited from among UKM undergraduate students at the Kuala Lumpur Campus based on the inclusion and exclusion criteria. Recruitment of volunteers will be conducted through advertisement. Simple random sampling will be used for participant selection, with those meeting the inclusion criteria being eligible for the study, while those meeting the exclusion criteria will be dismissed.

Before the commencement of the clinical trial, all participants will be provided with a consent form to review. The study will take place at the UKM Optometry Clinic, [name], Kuala Lumpur, Malaysia.

Participants will be required to attend the UKM Optometry Clinic for three sessions, each lasting 8 hours, during which they will wear FDA hydrogel contact lenses (groups I, II, III, IV, Va and Vb). Each lens will be placed on one eye only. Hence, the study will involve three wearing sessions, with the first session focusing on groups I and II FDA contact lenses, the second session on groups III and IV FDA contact lenses, and the third session on hydrogel silicone contact lenses Va and Vb. A 2-week rest period will be provided between each session. The complete study procedure is outlined as follows:

Care for Contact Lenses Leaflet.

Ensuring proper hygiene and technique is crucial to prevent eye health complications while wearing contact lenses. Subjects will receive thorough guidance on essential practices, including: maintaining hygiene care, correctly utilizing contact lens solution, applying and removing contact lenses, and adhering to permissible actions during wear. Additionally, subjects will be provided with a hotline for any inquiries or emergencies arising during contact lens use. Furthermore, they will receive a pamphlet titled "Soft Contact Lens Instructions" available at the UKM KL Optometry Clinic.

[figure not shown]

Figure 1 & 2. Soft contact lens use instructions

Pre-Assessment

A pre-assessment will precede the contact lens application during the initial session. The parameters measured will include these three tests: a) assessment of tear quantity using the Schirmer Test, b) evaluation of tear quality with the NIBUT Test, and c) examination of corneal staining using the Efron Grading Scale. These same tests will be conducted after the contact lenses have been worn for 8 hours and subsequently removed.

a) Tear Quantity Assessment (Schirmer Test)

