To assess tear quantity, the Schirmer test will be employed using a 5mm x 30mm Schirmer strip. The strip will be positioned in the temporal area of the subject's lower eyelid. The subject will be instructed to look upwards and blink naturally for 5 minutes, after which the Schirmer strip will be removed. The length of the wet portion of the strip will be measured and documented. Three readings will be obtained in millimeters (mm), and the average reading will be calculated for data analysis (Kallarackal et al., 2002).

b) Tear Quality Assessment (NIBUT Test)

The assessment of tear quality was conducted using the Non-Invasive Break Up Time Test (NIBUT) technique with the Bausch & Lomb keratometer. The subject was instructed to rest their

chin on the designated chin rest and align their forehead with the headrest. Initially, the subject blinked several times and then refrained from blinking. Time was measured from the last blink until the appearance of any distortion or break in the "mires." This time interval was recorded as the NIBUT measurement. If the subject blinked during the measurement, the test was paused briefly, and resumed after a few blinks. A one to two-minute break was provided between each measurement. Three readings were taken, and the average of these readings was utilized for subsequent statistical analysis (Mohidin et al., 2002).

c) Corneal Coloring Assessment (Efron Grading Scale)

The evaluation of corneal staining will involve using the Efron Grading Scale to assess any marks or damage on the subject's cornea before applying contact lenses. Initially, fluorescein dye will be applied to the subject's eyes using fluorescein strips moistened with saline solution. The subject will be instructed to look up, and the moistened fluorescein strip will be gently touched to the lower eyelid, followed by blinking. Using a biomicroscopic slit lamp equipped with a blue cobalt light, any staining or markings on the cornea will be examined. Any observed findings will be documented according to the Efron Grading Scale. Subsequently, the subject's eyes will be rinsed with saline solution to remove the fluorescein dye. The cornea will be divided into five zones (central, superior, inferior, temporal, and nasal) for recording observations, as depicted in Figure 1. The Efron Grading Scale, recognized for its suitability in assessing corneal coloring, will guide the evaluation process (Dundas et al., 2001; Woods & Fonn, 2018).

[figure not shown]

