Figure 3. Grading Scale Based on 5 Corneal Zones

i. Contact lens application

The placement of group I FDA contact lenses will occur on one side of the subject's eye, while group II FDA contact lenses will be positioned on the opposite side, with the positioning being randomized and unknown to the subjects. Researchers will delicately insert the contact lenses, providing clear instructions and precautions to the subjects regarding their wear. Subjects will be advised to remain near the UKM KL Campus throughout the contact lens application and return to the UKM Optometry Clinic after 8 hours for lens removal. Additionally, subjects will be instructed to promptly notify the researcher of any discomfort, pain, or unforeseen issues related to the wearing of contact lenses.

ii. Post-Wear Assessment

The researcher will remove the contact lenses from the subject's eyes. Subsequently, a postwearing examination of the contact lenses will be conducted. This examination mirrors the preuse assessment and includes a) evaluating tear quantity using the Schirmer Test, b) assessing tear quality with the NIBUT Test, and c) grading corneal staining based on the Efron Grading Scale. Following the removal of contact lenses, subjects will be required to complete the Contact Lens Discomfort Index (CLDI) questionnaire twice at each appointment: once for the right eye and once for the left eye. This allows for the measurement of comfort levels separately for each eye.

d) Contact Lens Discomfort Index Questionaires (CLDI)

The CLDI questionnaire will be employed to evaluate the comfort level during the usage of Group I and II FDA contact lenses. This questionnaire's selection of questions is rooted in the Contact Lens Dry Eyes Questionnaire (CLDEQ)-8. Known for its robustness and reliability, the CLDI questionnaire is specifically crafted to gauge comfort levels associated with contact lens wear (Arroyo-del Arroyo et al., 2022).

English version of the contact lens discomfort index (CLDI)

The Contact Lens Discomfort Index (CLDI) questionnaire is an easy instrument to measure the level of discomfort with the contact lenses.

Note: questions highlighted in grey correspond to the subscale score.

- Please, answer the following questions.
- 1. Since you have been wearing this type of contact lens, have you always worn them the same number of hours per day?
 - I currently use them more than previously (0)

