Subjects will be required to attend a second appointment following a rest period for the application of group III and IV FDA contact lenses. This appointment will involve the repetition of the procedure, including pre-application examination, contact lens wear, post-use examination, and subsequent rest period. The same procedure will be replicated for a third appointment involving the wearing of silicone hydrogel contact lenses Va and Vb.

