3.1.10 Flow Chart

3.1.11 Data Analysis

The forthcoming study will employ IBM SPSS Statistics Version 27 for data analysis. The normality of the data will be assessed utilizing the Shapiro-Wilk test. Subsequently, the distribution of the data will be examined accordingly.

Utilize the Paired t-test for normally distributed data or the Wilcoxon signed-rank test for non-normally distributed data to assess the disparities in tear quality and quantity before and after
 Employ the Paired t-test for normally distributed data or the Wilcoxon signed-rank test for non-normally distributed data to compare the mean quality and quantity of tears between FDA contact lens application groups I and II, groups III and IV, as well as silicone hydrogel materials A and B.

iii. Employ the Paired t-test for normally distributed data or the Wilcoxon signed-rank test for non-normally distributed data to assess the comfort levels associated with the application of FDA contact lenses within groups I and II, groups III and IV, as well as silicone hydrogel materials A and B.

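### The between-lens comparison of Schirmer and NIBUT makes no adjustment for each eye's same-session pre-wear reading; the planned test is valid, so only precision is at stake

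*Protocol*

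**What the plan says.** The second analysis item in Protocol section 3.1.11 uses a paired t-test, or a Wilcoxon signed-rank test if the data are not normal, "to compare the mean quality and quantity of tears between FDA contact lens application groups I and II". The same applies to groups III and IV and to the two silicone hydrogel materials. It names no covariate. Before-after change within a lens is the subject of a separate, preceding item.

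Section 3.1.9 describes the readings. Schirmer, NIBUT and staining are assessed before insertion, and "These same tests will be conducted after the contact lenses have been worn for 8 hours and subsequently removed". Each tear measure is an average of three readings. For Schirmer: "Three readings will be obtained in millimeters (mm), and the average reading will be calculated for data analysis". For NIBUT: "Three readings were taken, and the average of these readings was utilized for subsequent statistical analysis".

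For the second appointment, "This appointment will involve the repetition of the procedure, including pre-application examination, contact lens wear, post-use examination, and subsequent rest period", and the third follows the same procedure. A pre-wear value of each eye is therefore available in all three sessions. Lenses I and II go one to each eye, "with the positioning being randomized and unknown to the subjects".

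**The concern.** The two lenses of a session sit on the two eyes of one subject, so pairing already removes differences between subjects. What remains is the difference between a subject's two eyes, and part of that may exist before any lens is inserted. The pre-wear readings measure that part. A paired test on post-wear values ignores it, and the persistent part stays in the error term. With 16 evaluable pairs there is little precision to spare, and the information needed to recover some of it is already in the data set.

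The point concerns Schirmer and NIBUT only. The comfort questionnaire is completed after lens removal, so it has no pre-wear counterpart to adjust for.

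**Working it through.** **Inputs.** From section 3.1.4: 1.96 × 0.3 × 0.7 / 0.0025 = 164.64; 10% of this is 16.46, taken as 16; adding 2 for dropout gives 18. This reproduces the printed total with 1.96 entered unsquared, a separate matter that does not bear on this point. I use n = 16 pairs, and n = 18 as a check. The protocol states no power, SD or effect size for the between-lens comparison, so there is no planned figure to reproduce here. Assumed: two-sided alpha 0.05, and rho = 0, 0.3, 0.5, 0.7, where rho is the correlation of the pre-wear with the post-wear between-eye difference.

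**Unadjusted post-wear test.** Noncentral t with 15 degrees of freedom: 80% power is reached at 0.749 SD of the between-eye post-wear difference. At 0.75 SD the noncentrality is 0.75 × √16 = 3.0 and power is 80.1%, whatever rho is.

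**Adjusted test.** The lens effect is the intercept in a regression of the post-wear difference on the pre-wear difference. Its variance relative to the unadjusted test, including the cost of estimating the slope, is (1 − rho²)(n − 2)/(n − 3). At n = 16 the last factor is 14/13 = 1.077.

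| rho | Variance ratio, n = 16 | Variance ratio, n = 18 | Power adjusted, n = 16 | Power unadjusted, n = 16 |
|---|---|---|---|---|
| 0 | 1.00 × 1.077 = 1.08 | 1.07 | 77% | 80% |
| 0.3 | 0.91 × 1.077 = 0.98 | 0.97 | 81% | 80% |
| 0.5 | 0.75 × 1.077 = 0.81 | 0.80 | 87% | 80% |
| 0.7 | 0.51 × 1.077 = 0.55 | 0.54 | 96% | 80% |

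Adjusted power comes from 200,000 simulations (76.7%, 80.6%, 87.2%, 96.2%), with type I error 0.049 to 0.051. A noncentral-t approximation at 0.749 SD gives 76.6%, 80.4%, 87.3%, 96.4%. Break-even in variance is rho² = 1/14, so rho = 0.267.

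**Validity of the planned test.** In a null simulation with lens positions randomised (n = 16; rho 0.3, 0.5, 0.7), post-wear level, change score and adjusted analysis were all unbiased, with type I error 0.046 to 0.050.

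**Keeping the normality rule.** This check applied Shapiro-Wilk at 0.05 to the post-wear difference, with Wilcoxon on that difference if it rejects (20,000 simulations).
- Normal data: planned 80%, 79%, 80%, 80%; revised 77%, 80%, 87%, 96%.
- Heavy-tailed data (difference of lognormals, sigma 0.8): planned 88%, 87%, 86%, 85%; revised 87%, 88%, 90%, 93%.
- Type I error of the revised rule: 0.044 to 0.053.

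**Linearity.** For tear quantity, "the Schirmer test will be employed using a 5mm x 30mm Schirmer strip", so values could pile up at 30 mm. With 3% to 26% of eyes at the ceiling (assumed; 60,000 simulations), type I error stayed at 0.048 to 0.051. The power change against the paired t-test was about −3 to −4, 0, +6 to +7 and +16 to +17 points across the four values of rho.

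**If a change score is meant.** Write k for the ratio of pre-wear to post-wear SD of the between-eye difference. The variance of the change is 1 + k² − 2k·rho. The ratio of adjusted to change-score variance at n = 16 is then:
- k = 1: 0.54, 0.70, 0.81, 0.92.
- k = 0.7: 0.72, 0.92, 1.02, 1.08.

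The protocol gives neither k nor rho.

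**The case against.** The strongest reply is that nothing here is wrong. A paired test on fellow eyes with randomised lens position matches the design, is valid, and already removes between-subject variance. A more precise alternative under an unknown correlation does not turn the planned test into an error. That stands, and it limits the point to an optional improvement.

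Second, the gain depends wholly on rho. Section 3.1.7 excludes anyone with a history of ocular surface disease, so stable left-right differences may be small and rho low. At 0.3 the gain is about one power point, and below about 0.27 there is none. This also stands. Averaging three readings helps somewhat. If the true between-eye difference persists fully over 8 hours, rho of 0.27 needs a single-reading reliability of only 0.11 with independent reading errors, but 0.27 with fully shared errors. If the persistence correlation is 0.5, the figures are 0.28 and 0.53. These are conditions and do not show what rho is.

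Third, a reader might object that section 3.1.11 leaves open whether a post-wear level or a change is compared, and that objective ii in section 2.6.2 ("Contrasting tear evaluation and corneal staining pre- and post-8-hour application of FDA contact lenses") does not settle it. This should not be made a finding. It is detail that an SAP may fix, and because before-after change has its own item, post-wear level is the more natural reading.

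**Conclusion.** The point holds as a low-severity, precision-only improvement. At n = 16 and a lens difference of 0.75 SD, adjustment moves power from 80% to 77%, 81%, 87% or 96% for rho of 0, 0.3, 0.5 or 0.7. The worst case is about 8% more variance. These figures assume two-sided 0.05, normal data and a linear relation between the pre-wear and post-wear differences.

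Two stronger readings are tempting and are not supported. One is that the unadjusted comparison is biased or invalid: under randomised lens-to-eye positioning it is neither. Randomised positioning is written out for groups I and II; for the later pairs it follows from the repeated procedure. The other is that a change-score reading would cost, or gain, a definite amount of power. Any such figure needs the unknown ratio of pre-wear to post-wear variance as well as rho. With a pre-wear SD of 0.7 of the post-wear SD, adjustment is no better than a change score from about rho 0.5. No single power figure should be claimed for that reading.

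**What to change.** Reword the second item of section 3.1.11, for Schirmer and NIBUT and for each within-session lens pair, before data are seen. For each subject, form the between-eye difference in a fixed lens order (for example I minus II), both pre-wear and post-wear. The parametric comparison then regresses the post-wear difference on the pre-wear difference and tests the intercept as the lens effect. The pre-wear difference must be left uncentred, because centring it at its sample mean would turn the intercept back into the raw mean difference. Keep the planned Shapiro-Wilk rule and, when the data are non-normal, use the Wilcoxon signed-rank test on the post-wear between-eye difference. The before-after tests stay as they are.

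The cost is the wording of one item. Both readings are already collected, and the intercept test is standard SPSS regression output. The statistical price is one degree of freedom, about 3 power points if rho is near zero, and a linearity assumption that is worth a plot for Schirmer because of the 30 mm strip.

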Differences in water content within soft contact lenses may contribute to corneal dehydration, leading to dryness in the eyes. Despite advancements in soft contact lens manufacturing, instances of corneal allergies or sensitivities to such lenses have been reported (Moreddu et al., 2019). Studies suggest that changes in the tear film may occur within the first hour of contact lens wear, but quantitative data on tear film thickness post-application is lacking (Nichols et al., 2004).

Furthermore, there is limited data available for tear assessment, corneal staining, and comfort levels among FDA contact lens groups I, II, III, and IV, with recent studies predominantly focusing on silicone hydrogel lenses. Therefore, this study aims to compare tear quality and quantity, as well as comfort levels, between these contact lens groups and silicone hydrogel lenses.

While tear assessment before and after wearing silicone hydrogel lenses may reveal significant changes, no substantial differences are observed between different silicone hydrogel materials. However, factors such as water content, material composition, wearing duration, and lens deposition are more closely associated with corneal staining than contact lens care solutions, ocular surface characteristics, tear composition, demographics, or medical factors (Nichols & Sinnott, 2011).

In response to consumer needs, advancements in contact lens technology continue, with efforts aimed at enhancing wearer comfort. Innovations such as the incorporation of wetting agents, hydrophilic monomers, surface treatments, and water gradient surface technology are introduced to mitigate the impact of wearing silicone hydrogel lenses on the tear layer (Sulley & Dumbleton, 2020). Therefore, ongoing research into technological and material developments in contact lens manufacturing is essential to understand their effects on consumers and to facilitate future improvements.

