3.1.8 Instruments

- 1. Hydrogel soft contact lenses Group I, II, III, IV, Va and Vb
- 2. Schirmer Strip
- 3. Fluoresine Strip
- 4. Saline solution
- 5. Multipurpose solution Maxvue
- 6. Slitlamp Biomicroscope
- 7. Bausch & Lomb Keratometer
- 8. Contact Lens Discomfort Index Questionnaires (CLDI)

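### The stated aim of comparing hydrogel groups I–IV with silicone hydrogel lenses has no test in the analysis section, which compares lenses only within the same session

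*Protocol*

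**What the plan says.** Section 2.2 (problem statement) first notes limited data on tears, staining and "comfort levels among FDA contact lens groups I, II, III, and IV, with recent studies predominantly focusing on silicone hydrogel lenses". It then says that "this study aims to compare tear quality and quantity, as well as comfort levels, between these contact lens groups and silicone hydrogel lenses". Read together, the aim is groups I–IV against silicone hydrogel, for tear quality, tear quantity and comfort.

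Specific objective iii (section 2.6.2) concerns comfort before and after wear "among FDA contact lenses Group I,II, III, IV, and silicone hydrogel (Va and Vb"). This can be read as a comparison among all six lenses.

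Section 3.1.8 lists the six lenses: "Hydrogel soft contact lenses Group I, II, III, IV, Va and Vb". Section 3.1.9 pairs them by session, one lens per eye: "the first session focusing on groups I and II FDA contact lenses, the second session on groups III and IV FDA contact lenses". Va and Vb come last. Within a pair, the eye that gets each lens is randomised. The order of the sessions is the same for everyone.

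Section 3.1.11 names three analyses, each a paired t-test or Wilcoxon signed-rank test:
- tear quality and quantity before against after wear;
- tear quality and quantity "between FDA contact lens application groups I and II, groups III and IV, as well as silicone hydrogel materials A and B";
- comfort "within groups I and II, groups III and IV, as well as silicone hydrogel materials A and B".

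**The concern.** The aim crosses the lens classes and the listed tests do not. Every between-lens test stays inside one session, and each session holds either two hydrogels or two silicone hydrogels. Followed to the letter, the trial ends with no estimate and no test of hydrogel against silicone hydrogel.

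This is not a detail left to a separate analysis plan. The protocol names the software, the tests and the exact lens pairs, and it names the pairs twice.

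At stake is what the report can say. If the aim stays in place, a report might address it by noting that tears changed significantly with one lens and not with another. That does not show that the lenses differ.

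**Working it through.** **1. Pairs promised against pairs tested.** Inputs: six lenses (section 3.1.8); three tested pairs (section 3.1.11).
- All pairs: 6 × 5 / 2 = 15. Tested: 3.
- Hydrogel v silicone hydrogel, the pairs the section 2.2 aim concerns: 4 × 2 = 8. Tested: 0.
- The other untested pairs are 15 − 3 − 8 = 4 (I–III, I–IV, II–III, II–IV), all hydrogel against hydrogel.

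**2. What remains for tears.** Only the before/after tests, read here as one per lens, involve both classes. To see how badly a comparison of their verdicts performs, a sample size is needed. Section 3.1.4 works it as 1.96 × 0.3 × 0.7 / 0.0025 = 164.64; 10% of that is 16.46, taken as 16; adding 2 for dropout gives 18. The stated 18 is reproduced, and 16 is used below as the number completing.

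The protocol gives no SD, effect size or power for any outcome, so the true change (in SD units of the change) and the correlation between the two lenses' changes are assumptions. Both lenses are given the same true change. The simulation used 40,000 runs per row and a two-sided 0.05 level.

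| Assumed change | Correlation | Power of each before/after test | The two verdicts disagree |
|---|---|---|---|
| 0.3 SD | 0 | 20.6% | 32.8% |
| 0.3 SD | 0.5 | 20.6% | 23.6% |
| 0.5 SD | 0 | 46.7% | 49.6% |
| 0.5 SD | 0.5 | 46.6% | 34.3% |
| 0.7 SD | 0 | 74.8% | 37.5% |
| 0.7 SD | 0.5 | 74.5% | 26.9% |
| 0.9 SD | 0 | 92.1% | 14.6% |
| 0.9 SD | 0.5 | 91.6% | 11.8% |

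Check at zero correlation: disagreement = 2p(1 − p). With p = 0.467 this is 2 × 0.467 × 0.533 = 49.8%, in line with the simulated 49.6%. A direct paired test of the two changes declares a false difference in about 5% of runs throughout (4.9–5.2%).

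**3. What remains for comfort.** Section 3.1.9 lists three pre-wear tests (Schirmer, NIBUT, staining) and gives the CLDI only after lens removal. Section 3.1.11 has no before/after comfort test. So not even an indirect comparison of the two classes is planned for comfort, the outcome named in objective iii.

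**4. Whether adding the missing test is enough.** Groups I–IV are worn in sessions 1 and 2, Va and Vb in session 3, for every subject. The contrast of Va and Vb with I–IV is therefore identical to session 3 against sessions 1 and 2. A random subject-by-session term allows for two eyes sharing a visit. It does not remove a systematic difference between sessions.

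**The case against.** The best defence is that the analysis matches the design and only the wording of the aim is too broad. The research question (2.3), the hypothesis (2.4) and objectives i and ii are all framed as before and after wear, and objective iii can be read that way too. The conflicting sentence sits in the background. The three tested pairs are those the design supports, with both lenses worn on the same day and the side randomised. This largely stands, and it is why narrowing the aim comes first among the remedies. It does not remove the conflict: section 2.2 states the aim outright and no listed test serves it.

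Section 3.1.11 also suffered in extraction: the first item breaks off after its before-and-after wording. The items that name lens pairs are intact, so the missing words are unlikely to hide a test across the classes.

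Stronger readings are tempting but not supported:
- A reader might infer that 12 of 15 comparisons are missing. No section promises all 15 pairs, and none states an aim of ionic against non-ionic lenses. The gap that counts is the 8 pairs.
- A reader might compute that, with equal effects and 50% power, six before/after verdicts fail to agree in 1 − 2 × 0.5^6 = 97% of trials. That needs six independent tests, but the same subjects wear every lens. At a correlation of 0.5 between the test statistics it is about 1 − 2/7 = 71%, and at 90% power with independence 1 − (0.9^6 + 0.1^6) = 47%. It also counts any disagreement, not a split between the classes.
- A reader might infer that the protocol plans to compare p-values across lenses. It does not say so. This is a risk the gap leaves open for tears, and it cannot arise for comfort.

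**Conclusion.** The point holds as a mismatch between stated aim and listed analysis: 0 of the 8 hydrogel v silicone hydrogel pairs has a test. That count comes directly from the protocol and needs no assumption. The objective iii part is weaker, since it depends on reading that objective as a comparison among lenses.

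For tears, filling the gap by comparing before/after verdicts would show a spurious difference between two equally acting lenses in roughly 12–50% of trials, against about 5% for a direct test. The range rests on 16 completers, assumed changes of 0.3–0.9 SD, correlations of 0–0.5 and normal data. No single figure inside it can be defended from the protocol. For comfort, the question is simply left without a planned test.

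**What to change.** **Preferred.** Amend section 2.2 and objective iii so that between-lens conclusions are limited to I v II, III v IV and Va v Vb. State in section 3.1.11 that no between-lens conclusion will be drawn by comparing before/after p-values across lenses. The cost is wording and a narrower stated aim.

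**If the hydrogel v silicone hydrogel aim is kept.** Randomise the order of the three sessions for each subject, and add to section 3.1.11 one within-subject model per tear and comfort outcome:
- fixed effects: lens (six levels), eye and session (first, second, third);
- random effects: subject and subject-by-session;
- response: change from the same-session baseline for tear outcomes, post-wear score for comfort;
- one pre-stated contrast: mean of Va and Vb minus mean of I–IV.

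The cost is a randomised session order and one extra model per outcome, with no additional visits or subjects. The statement barring conclusions from separate p-values should go in here too.

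**If the order stays fixed.** Any such contrast must be labelled exploratory and confounded with session.
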